**Inclusion/Exclusion Criteria:** Once potentially eligible Veterans are identified and PCPs have granted permission to recruit, we will contact Veterans to identify those who meet study inclusion/exclusion criteria. Potential participants will be told that we are conducting a study to learn how Veterans can help other Veterans with chronic pain management, and that they will be randomly assigned either to the Veteran peer coach group or to the group receiving a pain self-management class. Eligible patients must 1) have musculoskeletal pain in the low back, cervical spine, or extremities (hip, knee, or shoulder) for  $\geq 3$  months; 2) have at least moderate pain severity, defined by pain  $\geq 5$  on a 0 (no pain) to 10 (worst pain imaginable) scale; and 3) indicate willingness to engage in phone or in-person contact on a regular basis with another Veteran. We have identified approximately 26,000 unique outpatients who meet criteria 1 and 2. Patients will be excluded if the electronic medical record indicates a diagnosis of a psychotic disorder (e.g., ICD-9 codes 295-295.9 for schizophrenia), current substance dependence (e.g., ICD-9 codes 304-304.9), severe medical conditions precluding participation (e.g., NY Heart Association Class III or IV heart failure, ICD-9 codes 428-428.9), or if the eligibility screener given to prospective participants reveals active suicidal ideation, severe hearing or speech impairment, or pending surgery for a musculoskeletal condition (e.g., back surgery).

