### **Data Analysis**

**Sample Size Determination.** Our sample size is calculated based on estimated intervention effect on the primary outcome, the Brief Pain Inventory (BPI) total score, a continuous measure. Effect sizes for the BPI in past studies by our team have ranged from .4 to .6. Because this is our first large-scale trial with peer coaches, we will conservatively power the study based on an effect size of .4. To test for a significant difference between the BPI change from baseline to the primary 6-month endpoint between the treatment and control arm, will use a linear mixed model. With a two-sided test and a Type I error of .05, we will have 80% power to detect a .4 effect size with 102 Veterans and 34 peer coaches in the treatment group and 80 Veterans in the control arm, assuming equal variance across the two treatment arms, 3 Veterans per peer coach, and an intra-class correlation (ICC) in the treatment group of .3, which was observed in IMPRESS. (A smaller N is required in the control group because they are not nested within peer coaches.) In our prior chronic pain trials at RVAMC, retention rates were >90%. With a conservative 15% attrition rate, we will need 120 (102/.85) Veterans in the treatment arm, 40

coaches, and 95 (80/.85) Veterans in the control arm, for a total N = 215 Veterans and N = 40 coaches. We plan an intent-to-treat analysis approach.

Consistent with previous studies at RVAMC, the sample will include at least 15% minorities, reflecting the demographics of our medical center. In our SCAMP study, Blacks comprised 16% of the Veteran sample and 13% in ESCAPE. We do not plan to over-sample minorities or power sufficiently to explore racial differences in treatment response. The racial/ethnic composition of RVAMC and participating CBOCs makes exploring racial differences in treatment response impractical unless we employed special efforts to recruit minorities other than Blacks.

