**Data Analysis for Aim 1.** We will summarize total BPI score at each time point (baseline, 6, and 9 months) for both study arms. To compare the primary outcome of total BPI score at each time point relative to baseline between two treatment arms, we will use a linear mixed-effects model fit to all time points. This model will allow us to compare the change in BPI from baseline to 6 months (primary endpoint) between treatment groups, while accounting for the correlation of measurements from the same Veteran/peer coach and adjusting for confounding factors. Fixed effects in the model will include an indicator for treatment group, time (baseline, 6, and 9 months.), treatment group by time interaction, and covariates found to differ significantly between treatment and control arm. Random effects will include a random patient-specific intercept and a random effect for peer coach within the treatment arm only. Additionally, the variance may be allowed to differ between treatment and control arms. Because this is a randomized trial design we do not expect covariates to significantly differ between the two groups. However, if there are statistically significant differences, these covariates will be included in the model. The linear mixed model for subject  $i$  in therapy group  $j$  at time  $k$  is

$$y_{ijk} = \beta_{10} + b_i + x_{ijk}'\beta + \gamma_{11}t_{ij1} + \gamma_{12}t_{ij2} + (1 - I_{ijk})r_{ijk} + (\beta_{20} + b_i + \gamma_{21}t_{ij1} + \gamma_{22}t_{ij2} + u_j + e_{ijk})I_{ijk}$$

where  $I_{ijk}$  is an indicator if patient is assigned to the treatment group,  $x_{ijk}$  is a vector of fixed covariates,  $t_{ij1}$  is an indicator for the 6-month time point,  $t_{ij2}$  is the indicator for the 9-month time point,  $b_i \sim N(0, \varepsilon^2)$  are patient-specific intercepts,  $\mu_j \sim N(0, \sigma_j^2)$  is the random effect due to peer coach  $j$ ,  $e_{ijk} \sim N(0, \sigma_T^2)$  and  $r_{ijk} \sim N(0, \sigma_C^2)$  are the residual errors for each treatment group. All analyses will include checking of assumptions and model fit. Our statistical model, which accounts for nesting of Veterans within peer coaches, will allow us to calculate the intra-class

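### The Aim 1 model forces equal variances and equal correlations across the three visits and cancels the coach effect from the change, so the standard error of the 6-month contrast can be wrong in either direction.

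*Combined protocol and SAP*

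**What the plan says.** Under Data Analysis for Aim 1, the BPI total is analysed jointly at all visits: "we will use a linear mixed-effects model fit to all time points". Time is categorical, with a treatment-by-time interaction, and the primary contrast is the difference between arms in change from baseline to 6 months. The random part is set out in one sentence: "Random effects will include a random patient-specific intercept and a random effect for peer coach within the treatment arm only".

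The printed equation adds three details:
- The coach effect carries a coach index but no time index.
- The two residual variances are indexed by arm, not by visit.
- There is no random slope, coach-by-time term or residual correlation.

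The section promises a general check of assumptions and fit. It names no alternative covariance and no robust standard error.

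The sample-size paragraph, by contrast, does charge for clustering. It assumes "3 Veterans per peer coach, and an intra-class correlation (ICC) in the treatment group of .3", with "102 Veterans and 34 peer coaches in the treatment group and 80 Veterans in the control arm". The Aim 2 text reuses the same model for the continuous secondary outcomes, and the BPI subscales use a similar one.

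**The concern.** A patient intercept with independent residuals gives every pair of visits the same correlation and every visit the same variance (apart from arm). The model then has one within-Veteran residual variance per arm. It uses that variance for the 0–6, 0–9 and 6–9 month differences alike, although the primary question concerns only the first. If the three differences are not equally variable, the primary standard error is an average of the right quantity and two wrong ones.

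The coach term raises a second issue. An effect that is constant over time is present at baseline too, so it drops out of any change from baseline. Coaching begins after baseline. If coaches differ in how much their Veterans improve, that variation reaches the 6-month change, but the model's standard error for the contrast has no term for it.

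At stake are the width of the primary interval and the true level of the primary test.

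**Working it through.** **Plan's own figure.** The plan gives no standard error or Type I error for this contrast. The nearest figure is the power statement: "With a two-sided test and a Type I error of .05, we will have 80% power to detect a .4 effect size". Using its inputs without a baseline correlation, the design effect is 1 + (3 − 1)(.3) = 1.6. SE = √(1.6/102 + 1/80) = 0.1679, and power = Φ(.4/0.1679 − 1.96) = 66%, not 80%. That shortfall is a separate matter. What matters here is that the plan's sizing includes a coach term and the primary contrast's model standard error does not.

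**Inputs.** From the sample-size paragraph: 102 Veterans with 34 coaches, 80 controls, 3 Veterans per coach, ICC .3, two-sided .05. Assumed: the correlations r06, r09 and r69 between visits, and unit standard deviation unless stated. Calculations are large-sample, with complete data.

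**Step 1: pooling over visit pairs, no coach effect.** Under compound symmetry the model's variance for any change is the mean of the three pairwise change variances. With equal standard deviations each pairwise variance is 2(1 − r), so

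model SE / true SE = √[(1 − mean of r06, r09, r69) / (1 − r06)]

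Type I error = 2[1 − Φ(1.96 × ratio)]

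| r06 / r09 / r69 (assumed) | SE ratio | Type I error |
|---|---|---|
| .5 / .5 / .5 | 1.00 | 5.0% |
| .5 / .5 / .6 | 0.966 | 5.8% |
| .5 / .5 / .7 | 0.931 | 6.8% |
| .5 / .5 / .8 | 0.894 | 8.0% |
| .5 / .35 / .71 (pure decay over 6, 9 and 3 months) | 0.980 | 5.5% |
| .6 / .5 / .7 | 1.00 | 5.0% |
| .6 / .5 / .6 | 1.041 | 4.1% |
| .7 / .5 / .6 | 1.155 | 2.4% |

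Worked case .5/.5/.7: the true variance is 2(.5) = 1.0. The pooled variance is (1.0 + 1.0 + 0.6)/3 = 0.867. The ratio is √0.867 = 0.931.

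**Step 2: a smaller baseline standard deviation alone.** Take all correlations .5 and baseline SD 0.8. The 0–6 and 0–9 variances are each .64 + 1 − .8 = .84, and the 6–9 variance is 1. The mean is .893, the ratio is √(.893/.84) = 1.031, and Type I error is 4.3%. With baseline SD 0.75 the ratio is 1.038 and Type I error 4.2%. Both are conservative.

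**Step 3: coach effect present only after baseline.** Keep total variance 1 at every visit. In the treatment arm, follow-up variance is then .3 (coach) plus .7 (Veteran). With Veteran-level correlation .5 throughout, the Veteran part of the change has variance 1 + .7 − 2(.5)√.7 = .863.
- True SE² = (.863 + 3 × .3)/102 + 1/80 = .01729 + .0125, so SE = 0.1726.
- Model: the pairwise variances in the treatment arm are 1.163, 1.163 and .7, with mean 1.009. SE² = 1.009/102 + 1/80, so SE = 0.1496.
- Ratio 0.87, Type I error 8.9%.

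With .6/.5/.55 the ratio is 0.89 and Type I error about 8%. Combining the coach effect with .5/.45/.7 gives a ratio of 0.83 and about 10%. At ICC .1 with correlations of .5, Type I error is 6.3%. If the coach effect is present equally at baseline, the ratio is 1.00 to 1.01 and nothing is lost.

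**The case against.** The strongest reply is that no direction can be read from the documents. They report no BPI standard deviation and no between-visit correlation, and Step 1 gives patterns in which the planned standard error is right or too large. This stands. A reader might infer that the interval is simply too narrow and the test anti-conservative, but the documents do not support that without conditions.

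Two arguments for that stronger reading are weaker than they look:
- **Unequal spacing.** Pure decay with time lowers r09 as well as raising r69, and gives only about 5.5%. The larger figures need follow-ups that correlate closely with each other without a lower 0–9 correlation. Lasting differences in response after baseline could produce this, but that is conjecture.
- **The entry rule.** Veterans must "have at least moderate pain severity", and one might expect this to narrow the baseline and inflate the error. Step 2 shows that a smaller baseline standard deviation alone does the reverse. The rule is also stated on a 0–10 pain scale that is not identified as the BPI total.

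Nor may the model be described as having only a patient intercept. It also has a coach effect and optional arm-specific variances, though neither relaxes the equal-variance, equal-correlation pattern over visits within an arm.

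The promise to check assumptions counts in the plan's favour. Without a named fallback, however, the covariance of the primary test would be chosen after the data are seen.

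On the coach term, the documents do not say whether the ICC of .3 refers to level or to change. If coach-related differences already existed at baseline to the same degree, the planned model would be adequate.

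**Conclusion.** The concern holds in conditional form. The planned covariance is restrictive, and the standard error of the primary contrast is right only if visits are equally variable and equally correlated and coach differences do not develop after baseline.

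Without a coach effect, the correlation patterns tabulated put the model standard error at 0.89 to 1.15 times the true one (Type I error 8.0% to 2.4%). With a coach effect arising after baseline at the planned ICC, it is about 0.87 to 0.89 times (about 8% to 9%), or 0.83 if the follow-ups are also closely correlated. All these figures rest on assumed correlations, and the coach figures also on reading the ICC as applying to follow-up scores.

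The coach term is the firmer ground for expecting too small an error. The sample size assumes clustering by coach, yet the written model removes it from the primary contrast. The change should be made because it is cheap and guards against error in both directions, not because inflation has been demonstrated.

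**What to change.** In Data Analysis for Aim 1, replace the patient intercept and independent residuals with:
- an unstructured 3×3 within-Veteran covariance over baseline, 6 and 9 months, separate by arm if it converges, with the fallback stated in advance (for example, one matrix common to both arms);
- a coach random effect in the treatment arm that acts on the 6- and 9-month visits;
- Kenward-Roger degrees of freedom for the treatment-by-6-month contrast.

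Rewrite the equation to match. The printed version includes the patient intercept twice for the treatment arm, probably a slip. It does not affect the change but should be corrected. If compound symmetry is kept instead, justify it with visit-specific variances and correlations from the team's earlier trials.

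The cost is SAP wording. A common matrix has six within-Veteran parameters in place of two (three if residual variances differ by arm), which is feasible with 215 Veterans. Convergence will need checking, and the interval may become wider or narrower. Sample size, visits and endpoint are unchanged, and the edit carries over to the subscales and the continuous Aim 2 outcomes.

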**Randomization.** Veterans will be randomly assigned to one of the two study arms using a table of random numbers generated by our statistician, [name]. To obtain the random treatment assignment for the 215 Veterans, five blocks of 43 Veterans will be used, and random treatment allocation will occur within each block to maintain the allocation ratio consistently across blocks. This block size is large enough to prevent investigators and research staff from guessing which treatment comes next in the sequence, while still allowing the allocation ratio to remain consistent.

**Data Analysis: Baseline Comparability.** Because of the size of this study, it is expected that randomization will produce treatment groups that are comparable and balanced. To test this assumption, we will tabulate baseline characteristics of participants and assess for potential imbalance in variables such as sociodemographics, depression, and anxiety across study arms. Additionally, descriptive statistics for baseline characteristics of peer coaches will be assessed (e.g., treatment history, including opioid use). Continuous variables will be assessed with graphical displays and summary statistics (means, standard deviation, range, etc.). Frequency distributions and percentages will be calculated for categorical data.

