correlation (ICC) in the treatment group to evaluate whether there are substantial variations among peer coaches. In secondary analyses, we will also look at the BPI subscales of pain intensity and interference separately, using a similar mixed-model approach and adjusting for multiple comparisons using the Šidák method to maintain the overall confidence at 95% and to adjust for multiple comparisons. To determine if fidelity moderates patient outcomes, we will include the peer coach fidelity score by treatment group interaction and the interaction (fidelity score by time by treatment group) for the 9-month time point in the model above.

**Data Analysis for Aim 2.** Secondary measures of self-efficacy, pain coping, patient activation, social support, and health-related quality of life are continuous measures; thus the linear mixed-effects model described above will also be appropriate to analyze these measures. If a linear mixed model does not seem appropriate for a given scale, then a generalized linear mixed-effects model will be used. Since there will be a number of secondary outcomes, we will use the Šidák method. Health care utilization (number of ED visits, hospitalizations, outpatient visits, telephone visits, and analgesic prescriptions, including opioids) over the 9-month intervention will be analyzed using a generalized linear mixed model, assuming the counts follow a Poisson or negative binomial distribution. Explanatory variables in the model will include treatment indicator and, if necessary, a random effect for peer coach within the treatment group only. Covariates that significantly differ between groups will be included. If counts include a high proportion of zeros, a zero-inflated count model may be required.

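### Baseline covariates enter the primary model without a time interaction, so the promised adjustment leaves the 6-month change contrast essentially unadjusted

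*Combined protocol and SAP*

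**What the plan says.** All of this is in the combined protocol and SAP, under Data Analysis.

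- **Primary contrast (Aim 1).** A linear mixed model is fitted to all three visits, with baseline BPI as one of the modelled outcomes. Its purpose is to "compare the change in BPI from baseline to 6 months (primary endpoint) between treatment groups", and to do so "while accounting for the correlation of measurements from the same Veteran/peer coach and adjusting for confounding factors".
- **Fixed effects (Aim 1).** After treatment and time, the list ends with "treatment group by time interaction, and covariates found to differ significantly between treatment and control arm". No covariate-by-time term is listed.
- **Trigger (Aim 1).** No imbalance is expected. "However, if there are statistically significant differences, these covariates will be included in the model".
- **Equation (Aim 1).** Covariates appear once, as x'β, where x "is a vector of fixed covariates". The coefficient β is the same at baseline, 6 and 9 months. Only the treatment indicator has its own visit terms (γ21, γ22).
- **What is screened (Baseline Comparability).** "we will tabulate baseline characteristics of participants and assess for potential imbalance in variables such as sociodemographics, depression, and anxiety across study arms".
- **Aim 2.** For the continuous scales, "thus the linear mixed-effects model described above will also be appropriate to analyze these measures".

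**The concern.** The endpoint is a change, but the covariate term acts on the level. A baseline value with a single coefficient raises or lowers all of a Veteran's scores by the same amount, so it says nothing about how far that Veteran moves between visits. If the arms differ by chance in depression, anxiety or another variable that predicts improvement, the plan's remedy is to add that variable. As written, that remedy hardly reaches the primary contrast.

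At stake is a primary result that could be described as adjusted for an imbalance which is still almost wholly present in the estimate. The BPI subscales and the continuous Aim 2 outcomes use the same kind of model. The utilization counts are not affected: they are modelled without visits, so a main effect does adjust there. The point concerns covariates other than baseline BPI, which the model already handles as an outcome.

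**Working it through.** The plan gives no figure for the effect of this adjustment, so there is none to reproduce.

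**Inputs from the documents.** Sample Size Determination: 102 and 80 Veterans analysed, 120 (102/0.85) and 95 (80/0.85, rounded up) enrolled, 40 coaches with 3 Veterans each, planned effect 0.4, two-sided 0.05. Missing Data: 10-15% attrition, with all observed outcomes used under MAR. Data Analysis for Aim 1: the model.

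**Step 1: algebra with complete visits.** Take a baseline covariate x_i. Apart from residual error, the model gives:

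- treated, baseline: β10 + β20 + x_i'β + patient and coach effects
- treated, 6 months: the same + γ11 + γ21
- change, treated: γ11 + γ21
- change, control: γ11

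The covariate, the patient intercept and the coach effect are all constant over time, so they all drop out of the change. A Veteran's mean over visits carries no information on γ21, because β20 is free. The estimate of γ21 is therefore the plain difference in mean change, with or without x. Arm-specific variances do not alter this. Nor does the printed equation's double appearance of b_i for treated Veterans.

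**Step 2: what remains.** Suppose change truly depends on x with slope δ, and the arms differ by D in mean x. The difference in mean change is then γ21 + δD. A main effect leaves δD in place; covariate-by-time terms estimate δ and remove it.

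**Step 3: simulation.** Trials of 120 + 95 Veterans were fitted by REML with a patient intercept, a coach effect in the treatment arm and arm-specific variances, 40 trials per scenario. Assumptions that are not in the documents: D = 0.35 SD, covariate effect on level 0.5, δ = 0.2 or 0, true effect -0.4. Baseline outcome variance was 0.25 + 0.35 + 0.40 = 1.00 in controls and 1.00 + 0.15 = 1.15 in the treatment arm, so units are close to SDs.

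| Scenario | No covariate | Main effect | Covariate × time | Main effect minus none: mean (largest in one trial) |
|---|---|---|---|---|
| Complete, δ = 0.2 | -0.3065 | -0.3065 | -0.3709 | 0.0000 (0.0000) |
| 15% dropout at random, δ = 0.2 | -0.3381 | -0.3444 | -0.4145 | -0.0063 (0.034) |
| 10% dropout related to x and baseline BPI, δ = 0.2 | -0.3330 | -0.3340 | -0.4007 | -0.0010 (0.048) |
| 15% dropout related to x and baseline BPI, δ = 0.2 | -0.3416 | -0.3377 | -0.3998 | +0.0039 (0.055) |
| 15% dropout related to x and baseline BPI, δ = 0 | -0.4031 | -0.3999 | -0.3998 | +0.0032 (0.047) |

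With complete data the mean SE was 0.1238 in all three fits. Where δ = 0.2, the time-interaction terms moved the estimate by 0.058 to 0.076 on average, against an expected δD = 0.2 × 0.35 = 0.07.

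**Step 4: size of the uncorrected part.** A just-significant imbalance (z = 2) at the analysed sizes is D = 2 × √(1/102 + 1/80) = 2 × 0.1493 = 0.299 SD. At the enrolled sizes, 1.96 × √(1/120 + 1/95) = 0.269 SD. With an assumed δ of 0.2 to 0.4 SD of change per SD of covariate:

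- 0.2 × 0.299 = 0.060; 0.060/0.4 = 15% of the planned effect
- 0.4 × 0.299 = 0.120; 0.120/0.4 = 30% of the planned effect

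In the complete-data simulation the shift was 0.064, about half the SE (0.064/0.124 = 0.52).

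**The case against.** **The data will not be complete.** This stands. A reader might infer that the covariates cannot touch the contrast at all. That is exact only if every Veteran attends every visit. The plan expects attrition and uses all observed outcomes, and under MAR a covariate related to both dropout and pain level has a small role as a main effect. The movement is slight, however, and it does not remove δD.

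**The covariate vector carries a time index k.** Formally this could hold follow-up values or interaction columns. But the listed fixed effects contain no covariate-by-time term, and the covariates are chosen by a check of baseline characteristics. Entering follow-up PHQ-8 or GAD-7 would adjust for post-randomization values, which is a different problem and one the plan does not propose. What stands is that the notation should be tightened.

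**Randomization already protects the estimate.** This also stands. A reader might infer that the primary analysis is biased. It is not: over repeated randomizations chance imbalance averages out and is reflected in the SE. The concern applies only when an imbalance occurs in a variable that predicts change, not merely level. The plan does not expect such an imbalance, and its default analysis without covariates is unaffected.

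**The main effect is harmless.** A reader might infer a loss of precision from the extra term. None appears in the SE.

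**Model checking might catch it.** The plan does promise checks of assumptions and fit, but these commit nobody to a covariate-by-time term.

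**Conclusion.** The concern holds, as a point that should be fixed rather than one that must be. The plan says the 6-month change comparison will be adjusted for confounding, and the specified term does not deliver that. With complete data the result is algebraic and rests on no assumed value: the contrast and its SE are the same with and without the covariate. With 10-15% attrition the simulated movement was below 0.007 SD on average and at most 0.055 SD in one trial.

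The size of the uncorrected shift is far less certain. The range of 0.06 to 0.12 SD, or 15-30% of the planned 0.4, rests on a slope that the documents do not supply. It also rests on matching SD units, because the plan does not say which SD standardizes the 0.4. It arises only if a chance imbalance occurs in a predictor of change.

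**What to change.** In Data Analysis for Aim 1:

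1. Name a short list of prognostic baseline covariates in advance, for example baseline PHQ-8 and GAD-7, which are already collected. Drop selection by significance tests of balance. Adding interactions while keeping that trigger would let a post-randomization test decide whether the primary estimate moves.
2. Write the covariates as x_i, baseline values only, so that follow-up values are excluded.
3. Give each covariate a main effect plus covariate × 6-month and covariate × 9-month terms.
4. State the same form for the BPI subscales and the continuous Aim 2 outcomes.

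The cost is SAP wording and two fixed-effect parameters per covariate beyond the main effect. No new data are needed.

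### The primary model equation counts the patient intercept twice for treated Veterans, against its own prose; coded as printed it would understate the peer-coach ICC and slightly widen the primary standard error

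*Combined protocol and SAP*

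**What the plan says.** Data Analysis for Aim 1 specifies the primary linear mixed model in prose and then in one displayed equation.

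- **Prose.** "Random effects will include a random patient-specific intercept and a random effect for peer coach within the treatment arm only". It adds that "the variance may be allowed to differ between treatment and control arms".
- **Equation, common part (both arms).** "y_{ijk} = \beta_{10} + b_i + x_{ijk}'\beta + \gamma_{11}t_{ij1} + \gamma_{12}t_{ij2".
- **Equation, part multiplied by the treatment indicator.** "\beta_{20} + b_i + \gamma_{21}t_{ij1} + \gamma_{22}t_{ij2} + u_j + e_{ijk})I_{ijk".
- **Distributions.** b_i has one normal distribution with variance ε² and no arm index. Residual variances are separate: σ_T² for treatment and σ_C² for control. The coach effect is u_j in the equation but μ_j where its distribution is given, and its variance is indexed by coach (σ_j²).
- **Use.** The model is to "compare the change in BPI from baseline to 6 months (primary endpoint) between treatment groups". It is also to supply the ICC in the treatment group, as the measure of how much coaches differ. The BPI subscales and the continuous Aim 2 outcomes use the same or a similar model.

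**The concern.** The equation and the prose describe different models. The prose has one intercept per Veteran. The equation doubles that intercept in one arm and so fixes the between-Veteran variance at a 4:1 ratio. Nothing in the plan motivates this ratio. The option of unequal variance is already met by the separate residual variances, and it would call for an estimated difference, not a fixed multiple. The sample size section assumes equal variance in the two arms.

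The equation is the only full statement of the primary model. A programmer who follows it literally would estimate one ε² that has to serve as ε² in controls and 4ε² in treated Veterans. The fit must then compromise. Control patient variance is fitted too low and the excess moves into the control residual. Treated patient variance is fitted too high and takes variance from the coach effect. At stake are the reported ICC and, to a lesser degree, the standard error (SE) of the primary contrast.

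**Working it through.** **1. Algebra on the printed equation.** With I = 0 the patient term is b_i, so its variance is ε². With I = 1 it is b_i + b_i = 2b_i, so its variance is 4ε². The ratio is 4. Without the b_i in the bracket it is 1.

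**2. The plan's own figure.** The plan states no variance component, so the sizes below cannot be checked against one. Its stated power is "80% power to detect a .4 effect size with 102 Veterans and 34 peer coaches in the treatment group and 80 Veterans in", where the last group is the controls. Taking unit variance and a design effect of 1 + 2 × 0.3 = 1.6, SE² = 1.6/102 + 1/80 = 0.02819, SE = 0.1679, and power = Φ(0.4/0.1679 − 1.96) = 66.4%. Reaching 80% needs a baseline correlation that the plan does not state. That is a separate matter; 80% serves here only as a reference for converting SE inflation into power.

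**3. Inputs for the size of the effect.**
- From the plan: 34 coaches × 3 Veterans, 80 controls, three visits, coach ICC .30.
- Assumed: patient variance of 0.4 to 0.6, the same in both arms.

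The printed structure (treated patient variance 4ε²) was fitted to these true covariances with separate residual variances. The single-intercept model returned the true values in every case in step 4.

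**4a. Equal total variance of 1 in each arm, coach variance 0.30, control residual larger than treated** (expected-likelihood fit):

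| Patient variance | True σ_T², σ_C² | Fitted ε² | Fitted coach variance | Fitted σ_T², σ_C² | Fitted ICC | SE ratio |
|---|---|---|---|---|---|---|
| 0.4 | .30, .60 | .150 | .234 | .296, .719 | .207 | 1.067 |
| 0.5 | .20, .50 | .222 | .171 | .198, .582 | .136 | 1.059 |
| 0.6 | .10, .40 | .307 | .090 | .100, .444 | .064 | 1.045 |

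First row:
- ICC = .234/(.234 + 4 × .150 + .296) = .234/1.130 = .207.
- The SE of the contrast is √(2σ_T²/102 + 2σ_C²/80). Fitted: √(.00580 + .01798) = .1542. True: √(.00588 + .01500) = .1445. The ratio is 1.067.

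**4b. Equal residual variances, true ICC .30** (patient variance ρ, residual 1 − ρ in both arms, coach variance .3/.7 = .429; REML on expected mean squares):

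| ρ | Fitted ICC | SE of contrast |
|---|---|---|
| 0.4 | .21 | +4.1% |
| 0.5 | .16 | +3.3% |
| 0.6 | .10 | +2.3% |
| 0.7 | .06 | +1.4% |
| 0.8 | .02 | +0.8% |

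**4c. True ICC .10.** The fitted ICC is 0 to about .015.

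**5. Conversion to power.** Power of 80% corresponds to a standardised effect of 1.960 + 0.842 = 2.802.
- SE +1%: 2.802/1.01 − 1.96 = 0.814, or 79%.
- SE +4%: 2.802/1.04 − 1.96 = 0.734, or 77%.
- SE +6.7%: 2.802/1.067 − 1.96 = 0.666, or 75%.

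**6. Dropout.** A small simulation (160 to 181 runs per scenario; 40 × 3 treated and 95 controls, 15% dropout) compared the printed and single-intercept models:
- Equal residuals, ρ = 0.6: mean SE 0.135 versus 0.132, coverage 98% versus 96%, ICC .11 versus .28.
- Equal total variance with true patient variance .2 treated and .5 control: mean SE 0.159 versus 0.146, coverage 97% versus 96%, ICC .16 versus .22.

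**The case against.** The best defence is that the prose already specifies the right model. The display has other slips of the same kind (u_j against μ_j, and the coach-indexed variance). Standard software asked for one random intercept per Veteran cannot produce 2b_i; someone would have to build a design column equal to 1 + I. The plan also promises checks of model fit. This stands: the harm is conditional on literal coding, and the plan does not show a decision to impose a 4:1 ratio. PDF extraction could in principle have altered the formula, although the bracket reads cleanly.

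A reader might infer that the primary result is invalid or its Type I error inflated. The documents do not support that. The primary contrast is change from baseline. In complete data b_i and u_j are constant over time and cancel, so the estimate is unaffected. The SE moves only through the residual variances, and under the printed equation it moves upward. If the arms shared one residual variance, which the prose leaves open, and the true residuals were equal, the inflation would be only 0.9 to 2.4% (patient variance 0.4 to 0.7).

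The direction of the ICC error also depends on a definition that the plan does not give. In the first row of 4a, using ε² instead of 4ε² in the denominator gives .234/(.234 + .150 + .296) = .344, above the true .30. The ICC is descriptive and decides no primary test. These points lower the severity. They do not remove the conflict between equation and prose, which no other section resolves.

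**Conclusion.** The point holds as a should-fix inconsistency. The printed equation gives treated Veterans four times the control patient-intercept variance, contradicts the single intercept in the prose, and is probably a slip.

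If coded literally:

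- **Coach ICC (main effect).** A true .30 would be read as about .06 to .21, and a true .10 as about 0, for assumed patient variances of 0.4 to 0.6 and with the fitted treated-arm variance as denominator. Higher patient variance makes it worse. The trial could report that coaches hardly differ when they differ as much as the sample size assumes.
- **Primary contrast.** The SE would be about 1-4% too wide with equal residual variances, and up to about 7% in the expected-likelihood fits if the control residual variance is larger. A nominal 80% power would become roughly 75 to 79%. In a further scenario where the true patient variance also differs between arms (.1 treated, .4 control), the figure reached 11%; no document supports that pattern. The direction is conservative throughout.

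The 4:1 ratio is exact. The other sizes rest on assumed variance components, because the documents give no BPI standard deviation or within-Veteran correlation. The simulation with dropout is small and supports the direction only.

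**What to change.** Delete b_i from the bracket multiplied by I_ijk, leaving the one in the common part. If unequal patient variance is intended, replace both terms with (1 − I)·b_iC + I·b_iT and estimate the two variances separately.

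In the same edit:

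- Use one symbol for the coach effect and give it one common variance σ_u² in place of the coach-indexed σ_j².
- Define the reported ICC from the stated components. With a single intercept this is σ_u²/(σ_u² + ε² + σ_T²); with arm-specific intercepts, use the treated-arm patient variance in place of ε².
- State that the fitted model has one intercept per Veteran, and check that the analysis code matches.

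The cost is a short correction of the equation and its code. Design, sample size and data collection do not change.
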